2.4.2. Subgroups for Safety Analyses

- Age categories: \leq 45 years, $>$ 45 years
- Type of NA at study entry (only for virologically suppressed participants):
 - Tenofovir Disoproxil Fumarate (TDF)
 - Tenofovir Alafenamide Fumarate (TAF)
 - Entecavir (ETV)
- Treatment history:
 - Currently not being treated
 - Virologically suppressed

2.5. Missing and Partial Dates Imputation Rules

For analysis and reporting purposes, missing or partial dates in adverse event (AE onset date; AE end date), HBV diagnosis and infection dates, concomitant therapies (start date; end date) will be

imputed according to the rules in the following subsections. The original, non-imputed, dates will be used only in listings.

2.5.1. Adverse Event Onset Date and Resolution Date

Partial AE onset dates will be imputed as follows:

- If the AE onset date is missing the day only, it will be set to:
 - The first day of the month when the AE occurred, if month/year of the AE onset date is different than the month/year of the first administration of study treatment date.
 - The day of the first study treatment administration, if the month/year of the AE onset date is the same as the month/year of the first study treatment administration but the month/year of the AE resolution date is different.
 - The earliest between the day of the first study treatment administration date and day of AE resolution date, if month/year of the AE onset are the same as both the month/year of the first study drug administration and the AE resolution date.
- If the AE onset date is missing both day and month, it will be set to the earliest of:
 - January 1 of the year of onset, as long as this date is on or after the first study drug administration.
 - Month and day of the first study treatment administration, if this date is in the same year of AE onset date.
 - December 31 if the AE onset date year is prior to the year of the first study drug administration.
 - The AE resolution date.
- Completely missing onset dates will not be imputed.

Partial AE resolution dates not marked as ongoing will be imputed as follows:

- If the resolution date of an AE is missing the day only, it will be set to the earliest of the last day of that month or the day of the date of death, if the participant died in that month.
- If the resolution date of an AE is missing both day and month, it will be set to the earliest of December 31 of that year or the day and month of the date of death, if the participant died in that year.
- Completely missing resolution dates will not be imputed.

2.5.2. HBV Diagnosis and Infection Dates

If the reported date is partially missing, the following imputation rules will be applied:

- the 15th of the month, if only the day is missing.
- the 30th of June, if only the year is available.
- No imputation if completely missing.

2.5.3. Concomitant Medication Dates

In case of partially missing concomitant medication start/end dates, the following imputation rules will be applied:

- the 15th of the month, if only the day is missing.
- the 30th of June, if only the year is available.
- If the imputed start date is after the concomitant medication end date, further adjustment of the imputed start dates is required. It will be imputed as the concomitant medication end date.
- No imputation if completely missing.

If the medication was taken prior to study start (DB Day 1) based on eCRF question, and the imputed start date is after first treatment date, further adjustment of the imputed start date is required. It will be imputed as the day prior to first treatment date.

If the medication was taken after study start (DB Day 1) based on eCRF question, and the imputed start date is prior to first dosing date, the imputed start date will be further adjusted to be the first study treatment dosing date. The partially missing medication end date will be imputed following the rule described at the beginning of this section to ensure it is on or after first dosing date, and after its start date.

In case of a completely missing start date, the concomitant therapy will be considered as having started before the trial, unless the eCRF indicates that the medication was taken after study start.

In case of a completely missing end date, the concomitant therapy will be considered as ongoing at the end of the trial, unless the eCRF indicates as not ongoing.

3. INTERIM ANALYSIS AND DATA MONITORING COMMITTEE REVIEW

The IDMC will conduct unblinded periodic data reviews to ensure the continuing safety of the study participants during the entire course of the study. The IDMC will also review the results of the primary and interim analyses (IAs) comprising cumulative safety and selected efficacy endpoints for providing the sponsor with further insight and interpretation of the data. The timepoints of the safety reviews, and further details on the safety data and selected efficacy (HBV disease blood markers) are specified in a separate document, the IDMC SAP. Details on the roles and responsibilities of the IDMC, as well as data reviews and the flows of communication, are documented in the IDMC charter.

The IA timepoints are described in the following section.

3.1. Interim Analyses

The primary analysis will be conducted at the time when all participants have completed Week 48 or discontinued earlier.

Interim analyses will be conducted to monitor safety and evaluate the time course of different disease markers to support the sponsor's internal decision-making, interactions with health

authorities, as well as inform decisions about additional studies and/or investigation of other treatment combinations. Three IAs are planned when:

- All participants have completed Week 60 visit or discontinued earlier.
- All participants have completed Week 72 visit or discontinued earlier.
- All participants have completed Week 96 visit or discontinued earlier.

One additional IA may be performed at the sponsor's discretion when all participants, who completed NA treatment at Week 48 of follow-up, have completed Week 120, i.e. Week 24 of the extended follow-up, or discontinued earlier. As all IAs follow the primary analysis, they will be conducted by the sponsor. Both primary and interim analyses will be based on all data available at the predefined cut-off time, including data at later time points for those participants who have reached subsequent visits

The final analysis will be performed when all participants have completed the last study visit or discontinued earlier.

This SAP covers the definitions of analysis sets, derived variables and statistical methods for the primary, interim and final analyses of this study.

3.2. Independent Flares Monitoring

Flares in this study will be adjudicated by the independent FLares Expert Panel (iFLEP). The iFLEP flare adjudication results are sent to the IDMC Chairperson, and the information will include conclusions and review history for each flare. Additional details are provided in the iFLEP Charter document. Flares are defined in Section [5.4.14](#).

4. SUBJECT INFORMATION

All the summaries will be done on the ITT analysis set unless specified otherwise for a specific display.

4.1. Disposition Information

The number and percentage of participants who are screened, screened failure and reason for that screening failure will be tabulated. Only an all participants group (total N) will be provided.

A summary of the number of participants randomized, randomized and not treated, in the safety, ITT, mITT, and PP sets, respectively, will be summarized by intervention arm.

Completion/withdrawal information, study disposition and treatment disposition will be summarized for the ITT, mITT, and safety sets (only for mITT and ITT set if the safety set is identical to ITT).

An overview of the study disposition will be provided by intervention arm and overall. The number and percentage of participants who completed or discontinued (or are ongoing [except the final analysis]) and the number and percentage of participants for each study discontinuation reason will

be summarized. The number and percentage of participants under each phase (i.e. double-blind study intervention phase, follow-up phase and Extended follow-up phase) will also be tabulated.

An overview of the treatment disposition will be provided. The number and percentage of participants who completed or discontinued study treatment or were ongoing at the time of the IAs cutoff (except the final analysis) will be presented by treatment and intervention arm. The incidences of treatment discontinuation reasons will also be summarized by study intervention arm for each treatment and overall.

A listing including information (i.e. the date of last study visit, the last study phase and time point [phase and week], the date of discontinuation and the reason) on participants which prematurely discontinue from the study and/or study treatment will be included. Information on the NA treatment completion, discontinuation and/or re-treatment will also be included.

4.2. Demographic and Baseline Characteristics

Tabulations of demographic and baseline characteristics will be presented by intervention arm and overall for the mITT, ITT and PP analysis sets. Continuous variables will be summarized by descriptive statistics (for example may include the number of participants, mean, standard deviation, standard error, median, range and interquartile range). Categorical/binary variables will be summarized by counts and percentages.

Additional summaries will be presented by the 2 randomization stratification factors (HBeAg status at screening and treatment history). The randomization stratification factors are reported by IWRS and also entered in the Electronic Case Report Form (eCRF). A cross-tabulation of the stratification factors collected by the IWRS vs. eCRF will also be provided by intervention arm to identify any mismatch. In case of discrepancies between the 2 sources, the randomization factors as entered in the eCRF will be used in the analyses/summaries.

4.2.1. Demographic Characteristics

The following demographic characteristics will be summarized by study intervention arm and overall.

- Sex: Male, Female
- Age (years)
- Age categories: ≤ 30 years, $> 30 - \leq 45$ years, > 45 years- ≤ 60 years, > 60 years
- Race: American Indian or Alaska Native, Asian (Japanese, Other Asian), Black or African American, Native Hawaiian or Other Pacific Islander, White, Not reported
- Ethnicity: Hispanic or Latino, Not Hispanic or Latino, Not Reported
- Region: Asia (China, Japan, and Other Asian Country), Europe, North America, South America
- Height at baseline (cm)
- Weight at baseline (kg)

- Body mass index (BMI) at baseline (kg/m^2) = weight at baseline (kg) / (height at baseline (m))² (rounded to 1 decimal)
- Body mass index group: Underweight <18.5, Normal ≥ 18.5 -<25, Overweight ≥ 25 -<30 and Obese ≥ 30
- History of Tobacco use: Yes/No

4.2.2. Baseline Characteristics

For the viral activity parameters (e.g. HBeAg, HBsAg, HBV DNA, HBV RNA, HBcrAg, anti-HBs antibody, anti-HBe antibody), baseline values are used unless specified differently.

- Duration of HBV infection (Years) = (date of randomization – date of HBV infection +1)/365.25; rounded to 1 decimal
- Time since HBV diagnosis (Years) = (date of randomization – date of HBV diagnosis+1)/365.25; rounded to 1 decimal
- Mode of HBV infection: Sexual transmission, intravenously injectable drug use, blood transfusion, Hemophilia-associated injection, occupational exposure, mother to child transmission, unknown and other
- Treatment history: not currently treated, virologically suppressed
- History of IFN-alpha (All participants): Yes, No
- History of Lamivudine, Telbivudine, Adefovir (All participants): Yes, No
- Has never received HBV treatment (only for currently not treated participants): Yes, No
- Type of NA at study entry (only for virologically suppressed participants): TDF, TAF, ETV
- HBeAg status at screening: positive, negative
- HBeAg at baseline (quantitative): values in IU/mL and log10 IU/mL (for HBeAg positive participants only)
- HBsAg at baseline (quantitative): values in IU/mL and log10 IU/mL
- HBsAg category at baseline (quantitative: IU/mL):
 - Participants with HBsAg <500 IU/mL
 - Participants with HBsAg <1,000 IU/mL
 - Participants with HBsAg <10,000 IU/mL
 - Participants with HBsAg $\geq 10,000$ IU/mL
- HBV DNA at baseline (quantitative): values in IU/mL and log10 IU/mL
- HBV DNA category at baseline (quantitative: IU/mL):
 - Participants with HBV DNA < LLOQ (20 IU/mL) target detected (TD) or target not detected (TND)
 - Participants with HBV DNA < LLOQ (20 IU/mL) target detected
 - Participants with HBV DNA < LLOQ (20 IU/mL) target not detected

- Participants with HBV DNA < 60 IU/mL
- Participants with HBV DNA < 2,000 IU/mL
- Participants with HBV DNA < 20,000 IU/mL
- Participants with HBV DNA < 100,000 IU/mL
- Participants with HBV DNA \geq 100,000 IU/mL
- HBV RNA (quantitative): values in copies/mL and log10 copies/mL
- HBV RNA category at baseline (quantitative: copies/mL):
 - Participants with HBV RNA TND
 - Participants with HBV RNA < limit of detection (LOD)
 - Participants with HBV RNA < 1000 copies /mL
 - Participants with HBV RNA < LLOQ
 - Participants with HBV RNA \geq LLOQ
- Hepatitis B core related antigen (HBcrAg) at baseline (quantitative): values in log U/mL
- HBcrAg category at baseline (quantitative: log U/mL):
 - Participants with HBcrAg <3 log U/mL
 - Participants with HBcrAg \geq 3 log U/mL-<4 log U/mL
 - Participants with HBcrAg \geq 4 log U/mL
- HBsAg Antibody (Anti-HBs) status at baseline (qualitative): Positive, Negative
- HBsAg Antibody (Anti-HBs) at baseline (quantitative): values in mIU/mL and log10 mIU/mL
- HBsAg Antibody (Anti-HBs) category at baseline (quantitative: mIU/mL):
 - Participants with Anti-HBs<10 mIU/mL
 - Participants with Anti-HBs \geq 10 mIU/mL
- HBeAg Antibody (Anti-HBe) status at baseline (qualitative): Positive, Negative
- Alanine Transferase (ALT) at baseline:
 - Baseline ALT values (U/L)
 - Baseline ALT toxicity grade according to DAIDS
 - Baseline ALT categorization (\leq 1.0 ULN, > 1.0 ULN to <2.5 ULN, \geq 2.5 ULN)
- Fibroscan score at baseline (quantitative: kPa)
- Fibrosis Stage: F0, F1, or F2
- HBV genotype (using the INNO-LiPA or sequence based HBV genotyping data): Genotype A, B, C, D, E, F, G, H, I, J, and Unknown

4.3. Medical History

A tabulation of the general medical history coded terms will be provided by body system class and by intervention arm.

4.4. Prior and Concomitant Medications

All medications will be coded using the World Health Organization-Drug Dictionary. Tabulations will include prior and concomitant medications which are defined as follows:

- (i) Prior medications are defined as medications with a start date occurring before the date of DB Day 1 regardless of when dosing of the medication ended.
- (ii) Concomitant medications are defined as medications received on or after DB Day 1, medication that was received before initial dosing and continued after initial dosing of the study interventions, or medication with missing stop date.

Medication that started before the DB Day 1 and continued afterwards will be summarized both as prior and, separately, as concomitant medication. All concomitant medications will be allocated to one or multiple analysis phases depending on their start date and end date and also taking into account the eCRF flag to indicate if it is taken before/after study start or still ongoing.

- (iii) Concomitant medications of interest include the following categories:

- Oral contraceptives (hormonal contraceptive of systemic use)
- Medications that impact immune system (e.g. corticosteroids, cyclosporin, interferon)
- Medications that can be subject to CYP3A4 induction or CYP3A4 inhibition

A frequency tabulation of prior medications, and concomitant medications will be shown by Anatomical Therapeutic Chemical (ATC) class level 2, level 4 and preferred terms by intervention arm. In addition, the concomitant medications and concomitant medications of interest will be summarized by analysis phase. A listing of prior medications, concomitant medications, and concomitant medications of interest, respectively, will be also provided.

4.5. Protocol Deviations

Only major protocol deviations will be summarized.

Protocol deviations and violations will be based on clinical review, but not limited to, the following criteria: (1) entered but did not satisfy criteria, (2) received wrong treatment or incorrect dose, (3) received a disallowed concomitant treatment, (4) developed withdrawal criteria but not withdrawn, (5) other. Protocol deviations will be closely monitored during the execution of the study and the final set of protocol deviation criteria will be finalized before the primary analysis database lock.

All major protocol deviations will be tabulated by coded term by intervention arm for the ITT analysis set. A listing of the major protocol deviations will be also presented.

A subset of major protocol deviations that may affect the assessment of efficacy (see list in **ATTACHMENT 1**) will be identified and finalized prior to database lock to define the Per-Protocol analysis sets 1 and 2 (Section 2.3). The number and percentage of ITT participants who are included in the PP1 and PP2 analysis sets will be summarized by intervention arm, accompanied by number and percentage of ITT participants who are excluded from the PP1 and PP2 analysis sets with the incidence of the major protocol deviations.

4.6. Extent of Exposure

Extent of exposure to study treatments will be summarized and presented based on the safety analysis set. The total duration of exposure during the DB phase will be calculated by each study treatment (JNJ-3989/ corresponding placebo, JNJ-6379/ corresponding placebo, and NA) separately and summarized descriptively by intervention arm. The duration of treatment with NA will be summarized also for the follow up phase by intervention arm.

Because of the different route and frequency of treatment administration across the 3 agents (for JNJ-3989 one subcutaneous injection once every 4 weeks, and for JNJ-6379 and for NA once daily tablet) the **total duration of exposure (weeks)** will be calculated for each agent as follows:

- JNJ-3989/placebo: [Min ((Date of last injection+27 days), Date of trial disposition, cut-off date) – date of first injection + 1] / 7
- JNJ-6379/placebo: [Min (Date of the last JNJ-6379/placebo administration, Date of treatment disposition for JNJ-6379/placebo, Date of trial disposition, Date of clinical cut-off)- first drug administration date + 1] / 7
- NA: [Min (Date of the last NA administration in the given phase, Date of discontinuation from NA, Date of trial disposition, Date of clinical cut-off) - first drug administration date in the given phase + 1] / 7

Cutoff dates will be defined to match the prespecified timepoints for IDMC periodical data reviews, interim analyses and the primary analysis, respectively (see Section 3).

The number and percentage of participants who skipped any dose of JNJ-3989/placebo or JNJ-6379/placebo or NA will be summarized separately for each study treatment by intervention arm during the DB phase. Additionally, the number and percentage of participants who missed 2 or more JNJ-3989/placebo injections, or who missed more than 5 JNJ-6379/placebo doses within a four week period, or who missed more than 5 doses of NA within a four week period.

For NA treatment, the total duration of exposure will be calculated separately for the DB and FU phases. For FU, the total duration will add up the weeks of NA treatment post-DB for those participants who did not stop NA prior to/at Week 48 and the NA re-treatment weeks, if any required. Those participants who stopped NA treatment at or before Week 48 and never restarted NA treatment thereafter will be counted as having zero weeks of NA exposure during the FU phase.

4.7. Treatment Compliance

Treatment compliance will be summarized for the safety analysis set by intervention arm for each study treatment except NA.

Treatment compliance (%) is defined as follows.

For JNJ-3989/placebo: (Total number of injections received/ 12) * 100%

For JNJ-6379/placebo: (Total medication intake / 4 *7 *48) * 100%

As the 250 mg daily dose of JNJ-6379/placebo consists of 4 tablets (2 tablets of 50 mg strength and 2 tablets of 25 mg strength), the denominator is 1,344 tablets= 4*7*48. The numerator representing the total medication intake for JNJ-6379/placebo is calculated as:

Total medication intake=(Total number of tablets dispensed–Total number of tablets returned)

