6. STUDY INTERVENTION

6.1. Study Intervention(s) Administered

Description of Interventions

Intervention name	JNJ-3989	Placebo for JNJ-3989	JNJ-6379	Placebo for JNJ-6379	Entecavir (ETV) monohydrate	Tenofovir disoproxil fumarate (TDF)	Tenofovir alafenamide (TAF)***
Dosage formulation	Solution for injection	Solution for injection	Tablets	Tablets	Film-coated tablets	Film-coated tablets	Film-coated tablets
Unit dose strength(s)	200 mg/vial	0.9% saline	25 and 100 mg		0.5 mg	300 mg**	25 mg
Dosage regimen	100 mg once every 4 weeks (Arms 1 and 3) 200 mg once every 4 weeks (Arm 2) 40 mg once every 4 weeks (Arm 4)	0.5 mL once every 4 weeks (Arms 5 and 6)	250 mg qd (Arms 1 and 5)	qd (Arms 2, 3, 4, and 6)	Nucleoside-naïve patients: 0.5 mg qd Lamivudine- refractory patients: 1 mg* qd (but should preferably be treated with TDF or TAF instead)	300 mg qd	25 mg qd
Route of administration	Subcutaneous injection (in the abdomen)	Subcutaneous injection (in the abdomen)	Oral	Oral	Oral	Oral	Oral
Dosing instructions	Regardless of food intake	Regardless of food intake	Regardless of food intake	Regardless of food intake	On an empty stomach	With food	With food

qd: once daily

^{*2} tablets of 0.5 mg
** 300 mg TDF is equivalent to tenofovir disoproxil 245 mg.
*** In countries where TAF is available, it will be one of the NA treatment options.

Physical Description of Study Interventions

The JNJ-3989 supplied for this study will be provided as an aqueous clear, colorless to light yellow solution with 200 mg/mL of JNJ-3989 for subcutaneous injection CCI

).

The JNJ-6379 supplied for this study is formulated as oral tablets containing command makes and makes and tablets containing command makes and tablets should be swallowed as a whole.

JNJ-3989 and JNJ-6379 will be provided under the responsibility of the sponsor. Refer to the IBs for a list of excipients. 13,14,15

The placebo for JNJ-3989 will be a solution for subcutaneous **EG**. The matching placebo for JNJ-6379 consists of the oral tablets without active drug substance (**EG** [placebo for **EG** mg] and **EG** [placebo for **EG** mg]).

The NAs ETV, TDF, and TAF are formulated as oral film-coated tablets of 0.5-mg, 300-mg, and 25-mg strength, respectively.

Packaging and Labeling

All study interventions will be packaged with each unit labeled with a unique medication ID number. Packaging and labeling of JNJ-3989, the corresponding placebo, and the NAs will be done in an open-label way.

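### SAP 4.7 divides compliance by the full 48-week course for everyone, so the percentage mixes early stopping with missed doses; its tablet description also contradicts the 250 mg dose

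*SAP*

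**What the plan says.** SAP Section 4.7 sets the scope: "Treatment compliance will be summarized for the safety analysis set by intervention arm for each study treatment except NA".

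For JNJ-3989/placebo the percentage is built on "Total number of injections received/ 12) * 100". For JNJ-6379/placebo the printed formula is "Total medication intake / 4 *7 *48) * 100", followed by the clarification that "the denominator is 1,344 tablets= 4*7*48". The numerator is a plain tablet count: "Total medication intake=(Total number of tablets dispensed–Total number of tablets returned". Neither formula has a term for how long the participant was on treatment, and the tablet formula has no term for strength.

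The same section says that the 250 mg daily dose "consists of 4 tablets (2 tablets of 50 mg strength and 2 tablets of 25 mg strength". The intervention tables in the protocol (Section 1.1 and Section 6.1) give the regimen as "250 mg qd (Arms 1 and 5" and list tablet strengths of 25 and 100 mg.

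Related summaries appear elsewhere in the SAP. Section 4.6 gives duration of exposure, counts of participants who skipped any dose, and counts above missed-dose thresholds. Section 4.1 gives treatment disposition with reasons for discontinuation.

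**The concern.** A compliance percentage is normally read as the share of prescribed doses that a participant took. With a fixed 48-week denominator it is that only for people who were prescribed all 48 weeks. Protocol Section 7.1 requires investigational treatment to stop in several situations, and those participants remain in the safety set. Their percentage falls because they stopped, whatever their adherence before that, and Section 4.7 does not say that the figure combines the two.

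At stake is how the compliance table is read. An arm with more early discontinuation will show lower compliance even if its participants never missed a dose. The table then partly repeats the disposition table under another name.

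The tablet description adds a second doubt. It contradicts the dose in its own sentence and the protocol tables, so a reader may wonder whether the denominator is right.

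**Working it through.** **Inputs.** Denominators of 12 injections and 1,344 tablets, and the SAP's tablet make-up: SAP 4.7. Dose 250 mg daily and strengths 25 and 100 mg: protocol 6.1. Injections every 4 weeks from Day 1 to Week 44: protocol Schedule of Activities. Course length 48 weeks = 336 days.

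**1. Reproduce the plan's figures.** Tablets: 4 per day × 7 × 48 = 1,344, as stated. Injections at Day 1 and Weeks 4, 8, …, 44 = 12, as stated.

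**2. Perfect intake, then an early stop.** Reported tablet percentage = (28 × weeks on treatment) / 1,344. Injections are counted as those due before the stop.

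| Stop at | Tablets taken | Reported | Injections taken | Reported | On-treatment adherence |
|---|---|---|---|---|---|
| Week 12 | 336 | 25% | 3 | 25% | 100% |
| Week 24 | 672 | 50% | 6 | 50% | 100% |
| Week 36 | 1,008 | 75% | 9 | 75% | 100% |

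**3. One number, two meanings.** A reported 80% is 0.80 × 1,344 = 1,075.2 tablets. That can be a 48-week completer who missed one dose in five, or a participant with perfect intake who stopped at 1,075.2 / 28 = 38.4 weeks.

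**4. Where the figure is sound.** A completer who misses 10% of whole daily doses is reported at 90%, has taken 90% of the planned dose, and has 90% on-treatment adherence. In an early stopper with no partial days, the percentage still equals the share of the planned 48-week dose received. In the Week 24 row, 250 × 168 = 42,000 mg of 250 × 336 = 84,000 mg is 50%.

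**5. Tablet strengths.** SAP make-up: 2 × 50 + 2 × 25 = 150 mg, which is 60% of 250 mg. Four tablets of 25 and 50 mg reach at most 4 × 50 = 200 mg. With 25 and 100 mg, solving 100a + 25b = 250 with a + b = 4 gives only a = 2, b = 2. Four tablets per day is thus the SAP's own count and is also compatible with the protocol strengths, so 1,344 does not move.

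**6. Equal counting of unequal tablets.** This assumes 2 × 100 + 2 × 25 mg per day, a split that the documents do not state.

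| Missed every day | By tablet count | By dose |
|---|---|---|
| One 100 mg tablet | 3/4 = 75% | 150/250 = 60% |
| One 25 mg tablet | 3/4 = 75% | 225/250 = 90% |
| Both 100 mg tablets | 2/4 = 50% | 50/250 = 20% |
| Both 25 mg tablets | 2/4 = 50% | 200/250 = 80% |

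Count and dose differ only when one strength is missed more than the other.

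**7. Printed formula.** Read left to right without brackets, full intake gives 1,344 / 4 × 7 × 48 × 100 = 11,289,600%. The sentence after the formula states the intended denominator, so this is typographical.

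**The case against.** The strongest reply is that percent of a planned course is a legitimate definition and that the rest of the SAP supplies what it leaves out. Section 4.6 gives duration and missed-dose counts for each agent, and Section 4.1 gives discontinuation and its reasons by arm. A careful reader can put these together. This is largely right and is why the point is minor. What it does not supply is a percentage of scheduled doses taken while on treatment, or any statement in Section 4.7 that its figure mixes stopping with missing.

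Some stronger readings are tempting, and the documents do not support them.

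- A reader might infer that the percentage measures neither dose nor adherence. Step 4 shows that it measures both correctly for completers who miss whole days.
- A reader might infer that the wrong strengths corrupt the result. The rule counts tablets, and the count is unaffected.
- A reader might infer that early stoppers are classed as non-compliant. Section 4.7 sets no threshold or category.
- A reader might infer that the percentage feeds the per-protocol sets or the comparison of Arm 1 with Arms 3 and 5. Attachment 1 uses missed-dose counts (items 17 to 19), and no such use of the percentage is stated.

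The extremes in step 6 need someone to omit one strength daily while taking the other. Nothing in the documents suggests this pattern, and Section 4.6 and Attachment 1 count missed JNJ-6379 doses, not tablets of one strength.

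**Conclusion.** The denominator point holds. As written, the rule understates adherence for anyone who stops early, in proportion to the part of the course not reached: 25%, 50% and 75% reported for perfect intake to Weeks 12, 24 and 36. The effect on an arm's summary depends on how many participants stop and when, which the documents do not forecast.

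The tablet description is a plain contradiction, 150 mg against 250 mg and against the protocol's listed strengths, but it changes no reported number. The missing brackets change none either.

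The measure is descriptive, so no hypothesis test, estimand or analysis set is affected. This is a worthwhile tidy-up, not a threat to the trial's conclusions. The step 2 results rest on the SAP's four tablets per day and the scheduled injections; only step 6 rests on an assumed tablet split.

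**What to change.** In SAP Section 4.7:

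- Define compliance as injections or tablets taken, divided by those scheduled from first dose to that participant's last scheduled dose or discontinuation.
- Keep the present calculation as a separate line labelled *percent of planned 48-week course received*.
- Reconcile the tablet description with the 250 mg dose in the same sentence and with the protocol intervention tables. This review does not say which text is right.
- Put brackets around the denominator, as (4 × 7 × 48).

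Weighting tablets by strength, with matching placebo tablets given their nominal strength, is optional and possible only if dispensing and return counts are held by strength. The denominator change does not depend on it.

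The cost is SAP wording and a small programming change using discontinuation dates that are needed anyway for Sections 4.1 and 4.6. No new data collection is needed for the main change.
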